9.6. Global Impression of Change

The SGIC and PGIC were only administered at post-baseline visits in Stages 3 and 4, starting from Month 3. Each answer connotes a change in the subject's status at the current visit relative to baseline. A ternary response variable is created as: "Improved" = score of 5 or higher, "No change" = score of 4, or "Declining" = score of 3 or lower. The number and percentage of subjects with the ternary response will be summarized at each visit.

9.7. Handling of Dropouts or Missing Data

The efficacy and safety analysis will be based on observed values. However, summary at the LAV will be provided for the efficacy analyses (see Section [6.5](#)).

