6. INTRODUCTION AND STUDY RATIONALE

6.1. Pompe Disease

Pompe disease, also known as acid maltase deficiency or glycogen storage disease type II, is an autosomal recessive genetic disorder caused by mutations in the gene that encodes acid α -glucosidase (*GAA*), an enzyme that catalyzes the breakdown of lysosomal glycogen. Pompe disease is also classified as a neuromuscular disease or a metabolic myopathy. It has an estimated global incidence of 1:40000 (Martiniuk, Chen et al. 1998; Ausems, Verbiest et al. 1999; Hagemans, Winkel et al. 2005a; Kemper, Hwu et al. 2007). Deficiency of *GAA* leads to the accumulation of glycogen in various tissues, particularly in striated muscles resulting in a broad spectrum of clinical manifestations that may present during infancy (infantile-onset Pompe disease [IOPD]) or in childhood, adolescence, or adulthood (late-onset Pompe disease [LOPD]). Earlier onset of disease and lower enzymatic activity are generally associated with a more severe clinical course (Kishnani, Steiner et al. 2006). The clinical features of the disease include progressive muscle weakness, respiratory insufficiency, and, in the case of IOPD, marked cardiomegaly, hepatomegaly, and cardiac failure (Hirschhorn and Reuser 2001; van der Ploeg and Reuser 2008). Late-onset Pompe disease can present at any age older than 12 months and is characterized by a lack of cardiac involvement and better short-term prognosis (Hirschhorn and Reuser 2001; Muller-Felber, Horvath et al. 2007; van der Ploeg and Reuser 2008). The symptoms are related to progressive skeletal muscle dysfunction. Proximal lower limb and paraspinal trunk muscles are usually affected first, followed by involvement of the diaphragm and accessory muscles of respiration. In some cases, diaphragmatic weakness may be evident before any other significant weakness is noted (Hagemans, Janssens et al. 2004; Hagemans, Winkel et al. 2005b). Most subjects with Pompe disease eventually progress to physical debilitation requiring the use of a wheelchair and assisted ventilation, with premature death often occurring due to respiratory failure (Hagemans, Janssens et al. 2004; Hagemans, Winkel et al. 2005a).

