6.4.3. Change from Baseline and Percent Change from Baseline

Analysis of change from baseline will include only subjects who have assessment at both baseline and the post-baseline time point being analyzed. That is:

- Change from baseline is calculated as: Change = post-baseline result – baseline result.
- Percent change from baseline is calculated as: $100 * (\text{Change from baseline} / \text{Baseline result})$.

If either the baseline or the post-baseline result is missing, the change from baseline and the percentage change from baseline are set to missing.

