^b Cohort 1 target day for Month X (starting from V9) is determined as (X * 30) + 43. For example, the target day for Month 3 is approximately at Day 3 * 30 + 43 = 133.

^c For safety analysis by visit, baseline is taken from Visit 9 (Day 85), but for efficacy, biomarker, and PRO analyses, baseline value is taken from Visit 2 (Day 1). See Section 6.4.1 and Section 6.4.5.

^d Tx is the target day of planned assessment visit at Month X.

- If the derivation starts from the original study day at V2, then: T_{MONTH X} = (30 * X + 127). For example, the target day at Month 54 = T_{MONTH 54} = 30 * 54 + 127 = 1747. Target day of the assessment visit immediately before Month X is given by T_{BEFORE}. For example, T_{BEFORE} = T₄₈ = (30 * 48 + 127) = 1567. Target day of the assessment visit immediately after Month X is given by T_{AFTER} = T₆₀ = (30 * 60 + 127) = 1927. The visit windows are then given as d1 – d2, where d1 = ([T_{BEFORE} + T_{MONTH X}] / 2) + 1 and d2 = (T_{MONTH X} + T_{AFTER}) / 2.
- If the derivation starts from Visit 9, then target day at Month X is given by T_{MONTH X} = (30 * X + 43). For example, the target day at Month 54 is T_{MONTH 54} = 30 * 54 + 43 = 1663. Target day of the assessment visit immediately before Month X is given by T_{BEFORE}. For example, T_{BEFORE} = T₄₈ = (30 * 48 + 43) = 1483. Target day of the assessment visit immediately after Month X is given by T_{AFTER} = T₆₀ = (30 * 60 + 43) = 1843. Visit windows are given as d3 – d4, where d3 = ([T_{BEFORE} + T_{MONTH X}] / 2) + 1 and d4 = (T_{MONTH X} + T_{AFTER}) / 2.

^e LAV represents the result obtained from the subject’s last visit of assessment. Summary at the LAV will only be provided for the efficacy analyses.

Efficacy data will be summarized at: Baseline (Visit 2), Visit 12, Month 3, Month 6, Month 9, Month 12, Month 15, Month 18, Month 21, Month 24, and every 6 months thereafter in Stage 4. Safety data will be summarized at: Baseline (Visit 9), Visit 10, Visit 11, Visit 12, Month 3, Month 6, Month 9, Month 12, Month 15, Month 18, Month 21, Month 24, and every 6 months thereafter in Stage 4.

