9.4.1. Motor Function Tests

Motor function tests (MFTs) will be summarized for all ambulatory subjects (that is, Cohorts 1, 3, and 4). The time in seconds (s) that the subject takes to accomplish each task (ie, Gowers' maneuver, 10MWT, 4-stair climb, chair test, and TUG) will be summarized. The assigned functional scores, which indicate the level of difficulty with which the subject performed the task, will be analyzed as continuous variables. The actual score, absolute change, and percent change from baseline in the test scores will be summarized.

The GSGC score will be analyzed as a continuous variable. The actual score, absolute change, and percent change from baseline will be summarized.

The 6MWD and % predicted 6MWD will be summarized for the actual value, absolute change, and percent change from baseline value. A listing of the data for each MFT including individual scores and summary scores will be provided.

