- Right/left knee extension – ambulatory patients only

Note: The muscle tests involving the upper body, lower body, total, and the proximal body (made up of the 5 moves from shoulder + hip) will be summarized.

4. Six-minute walk distance (6MWD) is the distance in meters (m) walked in the 6-minute walk test. It was performed by only ambulatory subjects.
 - Percent predicted 6MWD is calculated as:
$$\% \text{ predicted 6MWD} = (\text{actual 6MWD} / \text{predicted 6MWD}) * 100$$
(rounded up or down based on standard rounding rules), where the predicted values are derived for males and females using Enright equations ([Enright and Sherill, 1998](#)) as follows:
Males: $6\text{MWD} = (7.57 \times \text{Height in cm}) - (5.02 \times \text{Age in years}) - (1.76 \times \text{Weight in kg}) - 309 \text{ m}$
Females: $6\text{MWD} = (2.11 \times \text{Height in cm}) - (5.78 \times \text{Age in years}) - (2.29 \times \text{Weight in kg}) + 667 \text{ m}$
Height is measured at the Screening visit. Weight is weight at same date that the 6MWD was measured. If weight was not measured at that date, then the weight measurement closest to the given date will be used. Age is the age at the 6MWD assessment, and it is calculated as: $\text{FLOOR}([\text{age at assessment} - \text{birthdate}] / 365.25)$.
5. Gait, Stairs, Gowers', Chair (GSGC) total score is obtained by adding up the scores attributed to each of the following 4 functional tests:
 - Gait test is based on the 10-meter walk test (10MWT). This is scored as: 1 = normal; 2 = mild waddling, lordosis, and/or toe walking; 3 = moderate waddling, lordosis, and/or toe walking; 4 = severe waddling, lordosis, and/or toe walking; 5 = walks only with assistance (ie, braces, cane, crutches); 6 = stands, but unable to walk; 7 = confined to wheelchair.
 - Stairs test is based on the subject climbing 4 stairs. It is scored as: 1 = climbs four stairs without assistance; 2 = supports one hand on thigh; 3 = supports both hands on thighs; 4 = climbs stairs in upright position but with aid of railing; 5 = climbs while clinging to the railing with both hands; 6 = climbs only a few steps; 7 = unable to climb steps.

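### The SAP gives no value for an ambulatory subject who becomes unable to do the 6MWT or a timed test, so that subject leaves the visit means and LAV shows a value from before the loss

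*SAP*

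**What the plan says.** SAP 9.7 has two sentences on missing data: "The efficacy and safety analysis will be based on observed values", followed by "However, summary at the LAV will be provided for the efficacy analyses". Table 4, footnote e, in SAP 6.5.1 defines that row: "LAV represents the result obtained from the subject’s last visit of assessment". SAP 6.4.3 adds: "If either the baseline or the post-baseline result is missing, the change from baseline and the percentage change from baseline are set to missing".

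For the motor tests in Cohorts 1, 3 and 4, SAP 9.4.1 summarises "The time in seconds (s) that the subject takes to accomplish each task" for Gowers' maneuver, 10MWT, 4-stair climb, chair test and TUG. It also summarises 6MWD and percent predicted 6MWD as actual value, change and percent change. The assigned functional scores and the GSGC total are analysed as continuous variables.

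Appendix 1, item 5, codes inability in each GSGC component: for gait, "6 = stands, but unable to walk; 7 = confined to wheelchair"; for stairs, 7; for Gowers', 7; for chair, 6. Item 6 says a score is recorded alongside the time for TUG too, but prints no TUG scale. Item 4 gives 6MWD no value for a subject who cannot walk.

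**The concern.** Loss of ability is foreseeable here. Protocol 6.1 says "Most subjects with Pompe disease eventually progress to physical debilitation requiring the use of a wheelchair and assisted ventilation". The SAP visit windows run to Month 60 and beyond, and Cohort 4 could enter walking as little as 75 m (Protocol 9.2.1, criterion 32). A subject who can no longer walk or rise from the floor has no time, and may have no distance. Under the rules above, that subject drops out of the mean because of the outcome being measured.

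SAP 3.3 makes long-term efficacy a primary objective for Stages 3 and 4. There is no control arm and planned cohort sizes are about 5 to 11, so one omitted subject can change what a cohort's 6MWD row appears to say. The SAP does give rules for incomplete item responses on the RHS and FSS, but none for inability on a motor test.

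A parallel gap affects FVC, MIP, MEP and SNIP. SAP 4.4 defines these endpoints for subjects without invasive ventilatory support, so a subject who starts it leaves those summaries without being counted in them.

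**Working it through.** There is no design figure to reproduce: the study is descriptive and SAP 5.3.1 reports no sample size calculation. The check is a reading of the rules plus a sensitivity calculation.

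**1. Which planned summaries register inability**
- GSGC range from its item codes: minimum 1+1+1+1 = 4, maximum 7+7+7+6 = 27. This matches the stated 4 to 27, and the maximum is reached only when all four items are at their worst code. GSGC and the gait, stairs, Gowers' and chair scores therefore register inability.
- Seconds for all five timed tests: no value defined.
- 6MWD and percent predicted 6MWD: no value and no code.
- TUG: a score is mentioned, but its scale is not given.

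**2. Effect on mean 6MWD change if one subject is scored 0 m**

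Let *m* be the mean change of the other subjects, *n* the total number and *b* the affected subject's baseline. Then mean = ((n-1) x m - b)/n.

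Inputs are the Month 18 means in Protocol Table 6: Cohort 3, +49.0 m (n = 5); Cohort 1, +51.7 m, SD 45.9 (n = 9, against n = 10 at baseline). Eligible baselines in both cohorts are 200 to 500 m (Protocol 9.2.1, criteria 8 and 22). That one subject loses ambulation is an assumption.

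Cohort 3, four subjects at +49 m and one at 0 m; the observed-value table would show +49.0 m:
- b = 200: (196 - 200)/5 = -0.8 m
- b = 300: (196 - 300)/5 = -20.8 m
- b = 500: (196 - 500)/5 = -60.8 m

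Cohort 1, nine subjects averaging +51.7 m (sum 465.3) and one at 0 m; the observed-value table would show +51.7 m:
- b = 200: (465.3 - 200)/10 = +26.5 m
- b = 397.2 (the cohort's baseline mean): (465.3 - 397.2)/10 = +6.8 m
- b = 500: (465.3 - 500)/10 = -3.5 m

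**3. What LAV recovers**

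If LAV carries the affected Cohort 1 subject's last change *c*, the mean is (465.3 + c)/10. For assumed values of *c*:
- c = -50: +41.5 m
- c = 0: +46.5 m
- c = +42.2 (the cohort's Month 12 mean): +50.8 m

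LAV keeps the subject in the table but recovers little of the loss.

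**4. How far a single zero dominates**

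The observed Cohort 1 95% interval is 51.7 ± 2.306 x 45.9/√9 = 16.4 to 87.0 m. With the zero added at b = 397.2, the combined sum of squares gives SD 148.4 and an interval of -99.4 to 113.0 m. A mean that includes the zero is honest about the loss but very unstable, which argues for a supplementary summary and for showing the median.

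**The case against.** The strongest reply is that the plan shows decline elsewhere. A subject who stops walking moves the GSGC total and the item-score means toward worst. Every summary reports n (SAP 6.2.1), all efficacy data are listed by subject (SAP 9.4), and a declining category for PGIC and SGIC is tabulated by visit (SAP 9.6). This stands. A reader might infer that the SAP hides long-term decline or relies on observed values alone; the documents do not support that, because these outputs and the LAV row are all planned. What remains is narrower: a falling n does not say why it fell. Protocol 10.2 lets tests be deferred for illness or injury, and SAP 6.6 does not remap visits missed because of COVID-19.

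Second, Protocol 10.2 refers to a functional assessment manual that is not available here. If it records an impossible walk as 0 m, that zero is an observed value and already enters the 6MWD mean. This cannot be settled from the documents, so the point is conditional for 6MWD.

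Third, a reader might infer that every timed-test mean is biased toward benefit. That does not follow. The entry criteria do not require ability on Gowers' or stairs, so a subject unable at baseline who later succeeds has no computable change, and that omission works against the treatment. For 6MWD, minimum entry distances rule out inability at baseline, so the bias has one direction.

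Fourth, Table 6 shows Cohort 1 falling from 10 to 9 at Month 18. A reader might take this as a lost walker, but no reason is given, and data cut-off or withdrawal would explain it equally well. Cohort 3 stays at 5 throughout.

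Fifth, new ventilatory support may appear among the non-drug therapies (SAP 7.7). That is a partial cover and does not show how many subjects left the pulmonary tables.

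**Conclusion.** The SAP lacks a rule for inability on 6MWD and on times in seconds. On its text, a subject who loses ability leaves the visit mean, and LAV shows a result from before the loss. This rests on two conditions: that the assessment manual does not already record a value for inability, and that at least one subject loses ability during follow-up. The documents establish neither.

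If both hold, a single subject can matter. At Month 18 levels, one lost walker moves the Cohort 3 mean from +49.0 m to between -0.8 and -60.8 m, and the Cohort 1 mean from +51.7 m to between +26.5 and -3.5 m, over eligible baselines. These figures show sensitivity and are not estimates of what happened. The likely bias for 6MWD is toward stability or benefit; for timed tests it can go either way. The gap is worth closing before database lock, although GSGC, the item scores and the listings limit the harm.

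**What to change.** In SAP 9.4.1 and 9.7:

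1. For each motor test, tabulate at each visit and at LAV the number able, unable because of disease, and not done for other reasons. Take inability from the recorded item scores where they exist (gait 6 or 7, stairs 7, Gowers' 7, chair 6). State how it is identified for 6MWD and TUG, and what the assessment manual records.
2. Keep the observed-value tables. Add a supplementary summary with 6MWD set to 0 m for inability to walk, and speed set to 0 or a worst rank for inability on a timed test. LAV in that summary takes the unable value. Speed or ranks let gains of ability count as well as losses.
3. In the pulmonary function tables, count subjects who started invasive ventilation after baseline.

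The cost is SAP wording, a few extra tables and some programming; the item scores are already collected. With cohorts of about 5 to 11, one zero moves the mean strongly, so the median, already among the SAP 6.2.1 statistics, should be shown beside it. Whether zero scoring should become the main summary is debatable, and it is not needed to close this gap.

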9.8. Examination of Subgroups

Apart from the analysis by cohort, no other subgroup analyses will be conducted due to the small number of subjects enrolled in each study cohort.

10. SAFETY EVALUATION

All safety evaluations will be conducted on the Safety population using the summary statistics defined in Section 6.2.1 and presented as described in Section 6.2.2.3. By-visit safety summaries will be performed using the analysis visit windows defined in Section 6.5. Unscheduled visits will be included in all summaries, including the summaries that evaluate the PDLCs.

10.1. Missing Adverse Event Onset Date, Intensity, and Relationship

10.1.1. Missing or Partial Adverse Event Onset Date or Medication Start Date

Complete dates will be imputed from partial dates of AEs and medications solely for the purpose of defining treatment emergence for AEs and prior/concomitant status for medications. Dates will be defined using the hierarchy of derivations below.

Algorithm for imputing missing or partial AE or medication start date:

1. If year is not missing and is after the year of first application of study drug:
If month is missing, then impute month as January.
If day is missing, then impute day as the first of the month.
2. If year is not missing and is the same as the year of the first application of study drug:
If month is missing, then impute month as the month of the first application of study drug.
If day is missing but month is the same as the month of first application of study drug, then impute day as the first day of study drug application.
If day is missing but month is after the month of first application of study drug, then impute day as the first of the month.
3. If year is missing, then impute the year as the year of the first application of study drug:
If month is missing, then impute month as the month of the first application of study drug.
If day is missing, then impute day as the day of the first application of study drug.
4. If the start date is completely missing, but the AE is either ongoing or the stop date is after the first date of drug application, then impute the start date as the first application of study drug.
5. If using the above rules, the stop date is before the start date, then leave the start date missing and assume that AE is treatment-emergent for the purpose of the analysis.

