7.7. Prior and Concomitant Medications and Non-drug Therapies

Prior medications and non-drug therapies are defined as medications and non-drug therapies taken or occurring prior to the first dose of the study medication. These will be summarized 2 ways, as follows:

- Prior medications and non-drug therapies that were taken or occurring prior to the first dose of study medication (before Stage 1 Period 1). Note: These were reported in iCSR-1 and will not be repeated in this SAP, as the results are not expected to change.
- Prior medications and non-drug therapies that were taken or occurring prior to the first dose of the 20 mg/kg ATB200 + 260 mg AT2221 study medication (in Stage 2 Period 5, Visit 9).

Concomitant medications and non-drug therapies include medications with onset dates on or after the first dose of study medication, medications with onset dates prior to the first dose of study medication without a stop date, or medications with a stop date after the first dose of study medication. A single medication or therapy may be both concomitant and prior. These will be summarized by study stage, as follows:

- For Stage 1: Concomitant medications and non-drug therapies with onset dates on or after the first dose of study medication Stage 1, which will be presented by the SAD treatment dose
- For Stage 2: Concomitant medications and non-drug therapies with onset dates on or after the first dose of study medication Stage 2, which will be presented by the MAD treatment dose
- For Stages 3 and 4: Concomitant medications and non-drug therapies with onset dates on or after the first dose of the 20 mg/kg ATB200 + 260 mg AT2221 study medication (in Stage 2 Period 5)

Prior and concomitant medications and non-drug therapies will be coded to indication-specific Anatomical Therapeutic Chemical (ATC) classification and preferred name using the World Health Organization Drug Dictionary (WHODD, 01 MARCH 2020 DDE B3) and then summarized by level 4 ATC and preferred name using number and percentage of subjects on the Safety population. The summary will be based on the methodology described in Section [6.2.1](#) and presented as outlined in Section [6.2.2.3](#).

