7.8. Prior and Concomitant Pre-infusion Medications

Pre-infusion medications are medications administered to subjects prior to infusion with ATB200 to prevent IARs. Both prior pre-infusion medication (taken before the first dose of cipaglucosidase alfa IV infusion study drug) as well as concomitant pre-infusion medications taken during the study (ie, those that start on or after the first dose of study drug but before the last dose of study drug) will be summarized cumulatively by cohort (including total) for the Safety population.

For the prior pre-infusion medication summary, the presentation will include a row for the number (n) and percentage (%) of subjects who used any prior pre-infusion medications.

For concomitant pre-infusion medications (taken during study), the presentation will include rows for the:

- Number (n) and percentage (%) of subjects who used concomitant pre-infusion medications.
- Number (n) and percentage (%) of subjects who continued with their prior pre-infusion medications.
- Number (n) and percentage (%) of subjects who initiated at least 1 pre-infusion medication during the study (regardless of whether they had received that medication in the past).

A listing of all pre-infusion medications will be provided, and this display will include columns for subject ID, Cohort, ATC Level 4/drug name/report name, start date and time relative to original study Day 1, end date and time relative to original study Day 1, and dose (unit)/route/frequency. Flags will be added to this listing to indicate whether the medication was:

- Only used as a prior pre-infusion medication,
- Used as a concomitant pre-infusion medication,
- Used as both prior and concomitant pre-infusion medication, and
- Used as a concomitant pre-infusion medication that was initiated during the study (regardless of whether it had been used in the past) but not as a prior pre-infusion medication that continued on to become a concomitant medication.

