10.1.2. Missing or Partial Medication Stop Date

References to month are the month of the stop date:

1. If year and month are known and study medication stopped during that month and year, use the stop date of study medication.

2. If year and month are known and informed consent was provided during that month and year, use the date of informed consent.
3. If year and month are known and study medication stopped after the date of informed consent and not in the month that medication stopped, use the last day of the month.
4. If year and month are known and are prior to the month of informed consent, use the first day of the month.
5. If only year is known and study medication stopped during that year, use the stop date of study medication.
6. If only year is known and study medication stopped after that year, use December 31st of that year.
7. If only year is known and study medication stopped prior to that year, use the first day of the year.
8. Should any of the previous stop dates created be before a start date, either a complete date or an imputed one, use the (imputed) start date instead of the date that would otherwise be created.
9. Otherwise, if stop date is unknown, leave as missing.

No imputations will be applied to AE stop dates.

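### The SAP's date rules class a continuing medication with no recorded start date as concomitant only, and separately pull a partial consent-month stop back to consent

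*SAP*

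**What the plan says.** SAP 10.1.1 completes partial dates for adverse events and medications together, "solely for the purpose of defining treatment emergence for AEs and prior/concomitant status for medications". For starts:

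- Rule 3: "If year is missing, then impute the year as the year of the first application of study drug". It continues "If month is missing, then impute month as the month of the first application of study drug" and "If day is missing, then impute day as the day of the first application of study drug".
- Rule 2 leads to the same date when only the year is known and it is the first-dose year.
- Rule 5: "If using the above rules, the stop date is before the start date, then leave the start date missing". The classification that follows is given for adverse events only. Rule 4, on a wholly missing start, also names only adverse events.

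SAP 10.1.2 covers missing or partial medication stops. Rule 2: "If year and month are known and informed consent was provided during that month and year, use the date of informed consent". Rule 3 uses month-end for later months. Rule 8 moves a created stop that falls before the start forward to the start.

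SAP 7.7 sets the classes: "Prior medications and non-drug therapies are defined as medications and non-drug therapies taken or occurring prior to the first dose of the study medication". A drug is concomitant if it begins at or after first dose, or if it began earlier and has no stop or a stop after first dose. It can be both. SAP 7.8 has one row for subjects who carried on with an earlier premedication and another for "Number (n) and percentage (%) of subjects who initiated at least 1 pre-infusion medication during the study". It gives no date rule of its own.

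**The concern.** Moving an unknown onset to first dose is cautious for adverse events, because doubtful events are then counted as treatment-emergent. For medications the same move has no cautious direction. It asserts that the drug was not in use before the study, and this is least likely for a long-standing drug whose start nobody can recall. Two subjects on the same chronic drug would be classed differently only because one record carries a year.

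At stake are the prior-medication summary, the prior/concomitant flag in the listing and, by inference, the premedication rows. Protocol 11.1.3 says that a subject with an infusion-associated reaction should be premedicated at later infusions, so an on-study initiation can be read as a response to a reaction. A carried-over premedication miscounted as new would err against the product.

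The consent-month stop rule is a second, separate problem. First dose can follow screening by up to 28 days (Protocol 10.1.1), so a drug may be stopped after a first dose that falls in the consent month and still be given a stop before that dose.

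**Working it through.** The plan gives no figure to reproduce. The rules were applied literally to test records, using the SAP 7.7 definitions. Assumed dates: consent 3 May 2018, first dose 24 May 2018.

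| Record | Imputed dates | Status |
|---|---|---|
| A. Start unknown, ongoing | start 24 May 2018 (start rule 3) | concomitant only |
| B. Start unknown, full stop 5 Jan 2019 | start 24 May 2018 | concomitant only |
| C. Start known as 2012 only, ongoing | no rule applies; the year suffices | prior and concomitant |
| D. Start unknown, full stop 5 Apr 2018 | stop precedes imputed start; rule 5 leaves start missing | prior |
| E. Start 1 Jan 2012, stop May 2018, day missing | stop 3 May 2018 (stop rule 2) | prior only |
| F. Start unknown, stop May 2018, day missing | rule 5 first: start missing, stop 3 May; rule 8 first: both 24 May | prior, or concomitant only |
| G. Start unknown, stop Mar 2018, day missing | rule 5 first: start missing, stop 1 Mar; rule 8 first: both 24 May | prior, or concomitant only |

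**Start rule.** A and C can be the same drug with the same history, and only the completeness of the record differs. In SAP 7.8, record A would move from the continued row to the initiated row.

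**Stop rule.** In E, prior status is kept; what can be lost is concomitant status, and only if first dose falls in the consent month. With a uniform consent date and a uniform 1 to 28 day gap (both assumptions), that is about 52% of consent/first-dose pairs. Take consent on day 1 of a 30-day month, first dose on day f, and a stop day uniform over the month. The share of stops at or after first dose is then (30 - f + 1)/30:

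- f = 10: 21/30 = 70%
- f = 15: 16/30 = 53%
- f = 22: 9/30 = 30%

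Stop rule 2 classes all of these as prior only.

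**Cohort 1 anchor.** SAP 7.7 also summarises drugs taken before the first dose of the fixed regimen, which for Cohort 1 is Visit 9, Day 85 (SAP 6.4.5). If first application means Stage 1 Day 1, an unknown start is set to Day 1, before Day 85, and the drug stays prior to Period 5. If it means Visit 9, prior status is lost. SAP 10.1.1 does not say which. For Cohorts 2 to 4 the two dates coincide.

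**Size per subject.** Planned numbers are in SAP Table 2. One reclassified subject moves a percentage by 100/n points:

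- Cohort 1: 100/11 = 9.1
- Cohort 2: 100/6 to 100/4 = 16.7 to 25
- Cohort 3: 100/5 = 20
- Cohort 4: 100/8 to 100/6 = 12.5 to 16.7
- Total (11+4+5+6 = 26 to 11+6+5+8 = 30): 3.8 to 3.3

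**The case against.** The best defence is that little is affected, and that it can be seen. Protocol 10.2.3 asks for start and stop dates of drugs used to manage past infusion reactions, and 10.2.5 asks for dates of reported medications, so wholly missing starts may be few or none. The summary of drugs taken before Stage 1 Period 1 was reported in the first interim report and will not be repeated. SAP 12.3 displays partial dates with dashes, so a reader of the listings can spot them. No test is planned. All of this stands, and it limits the weight of the point, but it does not make the rule right.

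It can also be argued that rule 4, not rule 3, governs a wholly missing start. Rule 4 speaks only of adverse events, while the algorithm is introduced for medications too, so rule 3 is the natural reading for a medication.

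A reader might infer more than the documents support:

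- *That the consent-month stop rule also costs drugs their prior status.* It works the other way. An earlier stop keeps a drug prior, and it cannot turn a premedication with a known start into one begun on study.
- *That every unknown start loses prior status.* Record D shows otherwise: a full stop before first dose triggers start rule 5, and the stop itself shows prior use.
- *That a drug stopped in screening becomes concomitant only.* This needs an unknown start, a partial stop, and stop rule 8 applied before start rule 5. No order is stated.
- *That the initiated row is there to judge whether the product needs more prophylaxis.* No passage says so, and the row is defined without regard to past use. That 10.1.1 dates feed it is itself an inference from the lack of any other rule in 7.8.

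**Conclusion.** The point holds in limited form. Start rule 3 gives the wrong class to a medication with no recorded start that is ongoing or has a full stop at or after first dose: it loses prior status and keeps concomitant status. Stop rule 2 can remove concomitant status from a drug stopped after a first dose in the consent month. With both dates incomplete, the class depends on an unstated order of rules. For Cohort 1 the Period 5 result also depends on an unstated anchor.

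The effect is confined to descriptive medication and premedication summaries and flags. No adverse event or efficacy result changes through the medication rules. The total size cannot be given, because the number of incomplete records is unknown; each reclassified subject is worth about 9 to 25 points in a cohort column and 3.3 to 3.8 points in the total. The 52% and 30% to 70% figures rest on the uniform assumptions stated and are illustrations only. The change is worth making because the rules as written misclassify and correction costs almost nothing.

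**What to change.** For medications only:

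1. In SAP 10.1.1, treat a start with unknown year as prior, and also as concomitant unless the recorded stop precedes first dose.
2. In SAP 10.1.2, replace rule 2 with the last day of the stop month, or the last study dose if earlier, in line with rule 3.
3. State the order of start rule 5 and stop rule 8, and which first dose is the anchor for Cohort 1.
4. Say that these rules also govern SAP 7.8.

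Do not go further and set starts known only to the first-dose year to 1 January. With the true start uniform over the year and first dose on day D, the present rule wrongly removes prior status from (D - 1)/365 of such records: 16%, 33%, 49% and 74% at D = 60, 120, 180 and 270. Setting 1 January would wrongly add prior status to the remainder: 84%, 67%, 51% and 26%. That is worse whenever first dose falls before about mid-year.

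The cost is a few lines of SAP text and one derivation; SAP Section 2 allows changes before database lock. There are two downsides. A few drugs newly started on study with no start year will be counted as prior as well as concomitant. Month-end also credits concomitant status to some drugs stopped before a first dose in the consent month: by the formula above, 100% - 70% = 30% at f = 10 and 100% - 30% = 70% at f = 22. The case for month-end is therefore consistency with rule 3 and not hiding on-study use, rather than a lower error rate for every first-dose day.
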